### 7.1. Adverse Events

The analysis of AEs is based on the medical dictionary for regulatory activities (MedDRA) coded terms as provided in the clinical database. All reported AEs (solicited local, solicited systemic, and unsolicited) during the vaccination periods (Post-dose 1, Post-dose 2 and Regimen Phase) (ie, AEs following vaccination and AEs that have worsened since baseline) will be included in the analysis. Listings of AEs will include all reported AEs.

It is important to note that the AEs include any occurrence that is new in onset or aggravated in severity, toxicity grade or frequency from the baseline condition, or clinically relevant abnormal results of diagnostic procedures, including clinically relevant laboratory test abnormalities.

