9.2. Safety Evaluations

9.2.1. Safety Endpoints

Primary Endpoints:

- Adverse events, collected from signing of the ICF onwards until the 42-day post-boost visit (Day 71 in Group 1; Day 99 in Group 2; and Day 127 in Group 3).
- Serious adverse events and IREs, collected from signing of the ICF onwards until the end of the study.
- Solicited local and systemic adverse events (reactogenicity) until 7 days after each study vaccine administration.

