9.2.2. Safety Assessments

The study will include the following evaluations of safety and tolerability as described below and according to the time points provided in the [Time and Events Schedule](#). Any clinically significant abnormalities occurring from signing of the ICF onwards until 42 days after the boost vaccination must be recorded on the Adverse Event section of the CRF. Thereafter, reporting will be limited to all serious adverse events. Any clinically significant abnormalities (including those persisting at the end of the study/early withdrawal) will be followed by the investigator until resolution or until a clinically stable endpoint is reached (see Section 12). For reporting of IREs, refer to Section 12.3.3. Refer to Section 9.1.5 for more information for subjects in France who have further follow-ups from Day 365 onwards until the roll-over study is opened.

The investigators, together with the sponsor's medical monitor, will be responsible for the safety monitoring of the study, and will halt vaccination of further subjects in case any of the pre-specified pausing rules described in Section 9.2.3 have been met.

An IDMC will be appointed by the sponsor with recommendations from the Clinical Steering Committee (see Section 11.8) before the start of the study to perform regular review of the safety data during the study. Details regarding the IDMC are provided in Section 11.7.

Adverse Events

All adverse events, whether serious or non-serious, will be reported by the subject from signing of the ICF onwards until the 42-day post-boost visit. Thereafter, reporting will be limited to all serious adverse events and IREs up to the subject's last study-related procedure. Solicited local and systemic adverse events (reactogenicity, see below) will be reported by the subject until 7 days after each study vaccine administration. Adverse events will be followed by the investigator as specified in Section 12. Refer to Section 9.1.5 for more information for subjects in France who have further follow-ups from Day 365 onwards until the roll-over study is opened.

Solicited Adverse Events

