11.4. Safety Analyses

No formal statistical testing of safety data is planned. Safety data will be analyzed descriptively (including 95% confidence intervals, if applicable), by cohort and overall.

Baseline for all safety parameters will be defined as the last value before the prime vaccination.

Adverse Events (Including Reactogenicity)

The verbatim terms used in the CRF by investigators to report adverse events will be coded using the Medical Dictionary for Regulatory Activities (MedDRA). All reported adverse events (solicited local, solicited systemic, and unsolicited) will be included in the analysis. For each

adverse event, the number and percentage of subjects who experience at least 1 occurrence of the given event will be summarized by group. Summaries, listings, datasets, or subject narratives may be provided, as appropriate, for those subjects who die, who discontinue study vaccine due to an adverse event, or who experience a severe or a serious adverse event.

The analysis for solicited adverse events will be done on those subjects in the Full Analysis set for whom reactogenicity assessments are available in the database. The analysis of unsolicited adverse events will be done on the Full Analysis set.

Clinical Laboratory Tests

Laboratory abnormalities will be determined according to the toxicity grading tables, and in accordance with the normal ranges of the clinical laboratory. The most severe laboratory abnormalities following vaccination will be tabulated per regimen.

Vital Signs and Electrocardiogram

Vital signs and ECG abnormalities following vaccination will be tabulated by most severe abnormality grade.

Physical Examination

Physical examination abnormalities following vaccination will be tabulated by most severe abnormality grade.

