**Table 2: Analysis Periods**

Phase	Period	Interval	
		From	To
Screening		00:00 on the date of signing the informed consent form	One minute prior to Dose 1 administration on Day 1
Regimen*	Post-dose 1	Date and time of Dose 1 administration	Minimum of: a) 23:59 on the date of last contact (for early study discontinuations) b) 23:59 on the date of relative Day 29 Post-dose 1 c) one minute prior to Dose 2 administration
Post-dose 1 FU		One minute after the end of the Post-dose 1 period	Minimum of: a) 23:59 on the date of last contact (for early study discontinuation or completion) b) one minute prior to Dose 2 administration
Regimen*	Post-dose 2	Date and time of Dose 2 administration	Minimum of: a) 23:59 on the date of last contact (for early study discontinuation or completion) b) 23:59 on the date of relative Day 29 Post-dose 2  Note: subjects who do not receive Dose 2 will not have a Post-dose 2 period.
Post-dose 2 FU		One minute after the end of the Post-dose 2 period	23:59 on the date of last contact (for early study discontinuation or completion)

**Note 1:** \* Regimen period includes both the Post-dose 1 and Post-dose 2 periods.

**Note 2:** FU = follow-up.

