## 7. SAFETY

The safety and tolerability data include the following:

- AEs collected from signing of the informed consent form (ICF) onwards until the 42-day post-boost visit.
- Serious adverse events (SAEs) and immediate reportable events (IREs) from signing of the ICF onwards until the end of the study.
- Solicited local and systemic AEs (reactogenicity) recorded during the first 8 days (including the day of the vaccination) following each vaccination.

The safety and tolerability data will be summarized based on the full analysis set. The analysis will be based on the actual dose (ie, Dose 1 and Dose 2 for the prime and boost vaccinations, respectively) that the subjects received. For example, if Dose 2 is not administered to a subject, then that subject will not be included in the analysis of AEs in the Post-dose 2 period. Focus will be on safety signals detected during the Post-dose 1 and Post-dose 2 periods, as well as the Regimen phase.

- The safety data will be evaluated based on the pooled (matching on vaccination schedules) cohorts II and III. The data will be presented separately for Cohort I and Group 4. See

[Table 4](#) for an overview.

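### SAP 7.1 limits the AE analysis to periods closing at relative Day 29, so Grade 1–2 non-serious unsolicited AEs later in the primary-endpoint window may only be listed, and Section 3 does not declare this

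*SAP*

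**What the plan says.** Protocol 9.2.1 gives the first primary endpoint as "Adverse events, collected from signing of the ICF onwards until the 42-day post-boost visit", which it places at Day 71, 99 and 127 in Groups 1, 2 and 3. SAP 7 takes over the same window: "AEs collected from signing of the informed consent form (ICF) onwards until the 42-day post-boost visit". Protocol 11.4 states "All reported adverse events (solicited local, solicited systemic, and unsolicited) will be included in the analysis", with the number and percentage of subjects per event, by group. After the 42-day visit collection narrows: "Thereafter, reporting will be limited to all serious adverse events and IREs up to the subject's last study-related procedure" (Protocol 9.2.2).

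SAP 7.1 admits to the analysis "All reported AEs (solicited local, solicited systemic, and unsolicited) during the vaccination periods (Post-dose 1, Post-dose 2 and Regimen Phase", and then adds "Listings of AEs will include all reported AEs". In SAP Table 2 the Post-dose 2 period ends no later than "23:59 on the date of relative Day 29 Post-dose 2". Post-dose 1 has the matching limit and is also cut by Dose 2. Note 1 to that table composes Regimen from these two periods. Post-dose 1 FU and Post-dose 2 FU are separate phases outside it.

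SAP 7.1.3 orders SOC/PT tables over the whole reporting period for five categories only: SAEs, fatal AEs, AEs leading to permanent discontinuation from boost, Grade 3 AEs and IREs. SAP Section 3 lists two changes to the planned analysis, both to immunogenicity analysis sets.

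**The concern.** Safety is the only primary objective. The window named for its first endpoint is longer than the window the SAP analyses, and the SAP does not record the difference as a change. The sentence in 7.1 about listings sharpens the contrast: everything is listed, but only the named periods are said to enter the analysis.

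At stake is a basic figure for a vaccine safety report: the percentage of subjects with any unsolicited AE, and with a given preferred term at any grade, over the window the protocol calls primary. The uncovered stretch grows with the prime-boost interval, and SAP 1.4 says that many subjects were boosted late or not at all.

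**Working it through.** **Step 1: reproduce the endpoint days.** Boost days are 29, 57 and 85 (Protocol 6.1). Adding 42 gives 29 + 42 = 71, 57 + 42 = 99 and 85 + 42 = 127, as in Protocol 9.2.1.

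**Step 2: count analysed and unanalysed days from Dose 1.** For a boost on Day B (B ≥ 30), SAP Table 2 gives:

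- Post-dose 1: Days 1 to 29, 29 days
- Post-dose 1 FU: Days 30 to B − 1, B − 30 days
- Post-dose 2: Days B to B + 28, 29 days
- remainder of the endpoint window: Days B + 29 to B + 42, 14 days

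Days outside the analysed periods = (B − 30) + 14 = B − 16, out of B + 42. In Group 1 Dose 2 cuts Post-dose 1 short: Days 1–28 (28 days) plus Days 29–57 (29 days) are analysed, and Days 58–71 (14 days) are not.

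| Boost day | Analysed | Outside | Window | Share outside |
|---|---|---|---|---|
| 29 (Group 1) | 57 | 14 | 71 | 19.7% |
| 57 (Group 2) | 58 | 41 | 99 | 41.4% |
| 85 (Group 3) | 58 | 69 | 127 | 54.3% |
| 99 (lower bound, SAP Table 3 Group D) | 58 | 83 | 141 | 58.9% |
| 150 (assumed) | 58 | 134 | 192 | 69.8% |
| 200 (assumed) | 58 | 184 | 242 | 76.0% |

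The documents do not give the actual late-boost days. The ±3-day window on the 42-day visit (Protocol Table 3) moves the 14-day post-boost remainder to between 11 and 17 days. All shares are calendar days; the documents give no AE rates after Day 29.

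**Step 3: which events are exposed.** Five categories have whole-period tables (SAP 7.1.3). Solicited AEs always go to Post-dose 1 or Post-dose 2 (Attachment 1). Attachment 1 also moves some FU-phase events into an active period: overlapping or consecutive events with the same preferred term that began there (Step 2, rule 3), and some events with partial or missing start dates (Step 1). What remains is Grade 1–2, non-serious, non-IRE unsolicited AEs with a known start in an FU phase.

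**Step 4: the looser reading.** Suppose FU phases get their own columns. Take Groups 2 and 3, with an assumed 10% of subjects in each of the four period and phase columns and the same denominator throughout. The cumulative percentage then lies between 10% (the same subjects each time) and 40% (all different). The Regimen column de-duplicates only the two active periods. If it shows R%, with R between 10 and 20, the cumulative figure lies between R and R + 20, so a 20-point range remains.

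**The case against.** The strongest reply is that the SAP does not clearly exclude the FU phases. SAP 7.1.3 presents AEs by period or phase, Table 2 names both FU phases, Attachment 1 allocates unsolicited AEs to every period and phase, and SAP 7 says "Focus will be on safety signals detected during the Post-dose 1 and Post-dose 2 periods, as well as the Regimen phase", which is emphasis rather than exclusion. That reading has real support. If it is the intended one, the events are tabulated and only the de-duplicated figure is missing. But 7.1 is the sentence that says which AEs enter the analysis, and it points the other way, so the text has to be settled.

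A second reply is that Protocol 9.2.1 defines a collection window, Protocol 11.4 does not promise a single cumulative table, and Protocol 11 leaves detail to the SAP. This stands as far as splitting by period goes. It does not cover leaving collected AEs out of every summary table, which conflicts with Protocol 11.4.

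A reader might infer more than the documents support:

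- **That no term or severity percentage exists over the window.** Not so for Grade 3 AEs, SAEs, fatal AEs, IREs and AEs leading to boost discontinuation. Non-serious, non-IRE collection stops at the 42-day visit, so for a non-serious Grade 3 AE the whole-period table essentially covers the endpoint window.
- **That late follow-up would swamp a Post-dose 2 FU column.** That phase runs to last contact, but ordinary unsolicited AEs in it can come only from the days up to the 42-day visit. Later time adds only SAEs and IREs.
- **That schedules are compared unfairly.** Analysed time is 57, 58 and 58 days, so the existing tables are close to balanced.
- **That data are lost.** All reported AEs are listed.

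**Conclusion.** The point holds in a limited form and should be fixed. Followed literally, SAP 7.1 leaves Grade 1–2, non-serious, non-IRE unsolicited AEs starting in an FU phase out of every summary table of the first primary endpoint, apart from AEs leading to boost discontinuation and those Attachment 1 reallocates. On the looser reading they are tabulated, but no de-duplicated any-grade percentage covers the endpoint window. Section 3 is silent either way.

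The planned-schedule size is 20%, 41% and 54% of post-prime window days in Groups 1, 2 and 3, and at least 59% for a boost on Day 99 or later. These figures rest on the Table 2 definitions and on-time 42-day visits. They are not shares of missed events, which the documents do not allow anyone to estimate. Never-boosted subjects raise a related gap that starts in Protocol 9.2.1: Table 2 gives them Post-dose 1 and Post-dose 1 FU, but their AE window is tied to a visit they do not have. Group 4 is not assessed, because its France-specific protocol was not available.

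**What to change.** - Keep the existing tables that close at relative Day 29; they suit comparison across schedules.
- Amend SAP 7.1 to include FU-phase unsolicited AEs up to the 42-day post-boost visit, and use the term for post-vaccination AEs in one sense in 7.1, 7.1.3 and Attachment 1.
- Add one SOC/PT table set of unsolicited AEs (number and percentage, by severity and relatedness) from Dose 1 to that visit, by schedule and vaccine. State that AEs between consent and Dose 1, which also fall in the protocol window, are listed separately, and footnote the unequal lengths (71, 99 and 127 days, longer for late boosts).
- State the window end used for never-boosted subjects.
- Record any remaining departure from Protocol 9.2.1 or 11.4 in Section 3.

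The cost is SAP wording and one extra table set from data already collected. The downside is that crude percentages in the new tables are not directly comparable across schedules, because the windows differ in length.

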### **7.1.1. Definitions**

Solicited AEs are precisely defined events (local and systemic) that subjects are specifically asked about and which are noted by subjects in the diary. All other AEs are considered unsolicited. Refer to Sections 9.2 and 12.1.1 of the CTP for further details.

#### ***Solicited Local (Injection Site) Reactions***

The analysis of local solicited AEs will include:

- Pain/Tenderness
- Erythema
- Induration/Swelling
- Itching at injection site

#### ***Solicited Systemic Adverse Events***

The analysis of systemic solicited AEs will include:

- Fever (defined as body temperature of 38°C or higher)
- Headache
- Fatigue/Malaise
- Myalgia
- Nausea/Vomiting
- Arthralgia
- Chills

#### ***Serious Adverse Events***

SAEs will be collected from signing of the ICF until the end of the study. An SAE based on the International Council for Harmonization (ICH) and the European Union (EU) Guidelines on Pharmacovigilance for Medicinal Products for Human Use is any untoward medical occurrence that at any dose:

- Results in death
- Is life-threatening (the subject was at risk of death at the time of the event. It does not refer to an event that hypothetically might have caused death if it were more severe.)
- Requires inpatient hospitalization or prolongation of existing hospitalization
- Results in persistent or significant disability/incapacity
- Is a congenital anomaly/birth defect
- Is a suspected transmission of any infectious agent via a medicinal product
- Is medically important\*.

\*Medical and scientific judgment should be exercised in deciding whether expedited reporting is also appropriate in other situations, such as important medical events that may not be immediately life-threatening or result in death or hospitalization but may jeopardize the subject or may require intervention to prevent one of the other outcomes listed in the definition above. These should usually be considered serious.

### ***Immediate Reportable Events***

The following list of neuroinflammatory disorders are categorized as IRE, and should be reported to the sponsor within 24 hours of after becoming aware of the event using the IRE Form. Relevant data from the IRE form will be captured in the clinical database.

- Cranial nerve disorders, including paralyse/paresis (eg, Bell's palsy)
- Optic neuritis
- Multiple sclerosis
- Transverse myelitis
- Guillain-Barré syndrome, including Miller Fisher syndrome, Bickerstaff's encephalitis and other variants
- Acute disseminated encephalomyelitis, including site specific variants: eg, non-infectious encephalitis, encephalomyelitis, myelitis, myeloradiculomyelitis
- Myasthenia gravis and Lambert-Eaton myasthenic syndrome
- Immune-mediated peripheral neuropathies and plexopathies (including chronic inflammatory demyelinating polyneuropathy, multifocal motor neuropathy and polyneuropathies associated with monoclonal gammopathy)
- Narcolepsy
- Isolated paresthesia of >7 days duration

### ***Causality***

The solicited local AEs will be considered as related to the study vaccine, by definition. The unsolicited and solicited systemic AEs will be considered as related to the use of the study vaccine if the attribution is possible, probable or very likely. An AE will be considered not related with the use of the study vaccine if the attribution is not related or doubtful. Refer to Section 12.1.2 of the CTP, for further details.

### ***Severity Criteria***

The severity of the AEs is classified by the investigator as mild, moderate or severe using the Division of Microbiology and Infectious Diseases (DMID) Toxicity Table for Use in Trials Enrolling Healthy Adults (Attachment 3).

Solicited events that are graded less than mild, are not considered AEs. For some solicited events (eg, induration/swelling), the diameter and grading (as reported by the investigator [ie, functional grade]) are collected in the electronic case report form (eCRF). The diameter will be used to derive the toxicity grading. The worst grade should be used when both the diameter derived

grade and the investigator-reported grade are available. If either the diameter-derived or the investigator-reported grade is available, then this should be used.

### 7.1.2. Data Handling Rules

Missing data will not be imputed. If the severity is missing for a solicited AE, then it will not be considered as an AE. If relationship of AEs to the study vaccine could not be derived (ie, missing or unknown), it will be considered as unknown, for analysis purposes. Local solicited AEs will be considered as related with the use of the study vaccine, by default.

Solicited events will always be allocated to the analysis period (Section 2.1). For analysis purpose, the AEs will be allocated to periods and/or phases as described in Attachment 1.

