## 2. TRANSFORMING ON-SITE ASSESSMENTS AND DIARIES OF SOLICITED ADVERSE EVENTS INTO AN ANALYSIS FORMAT

When creating the analysis dataset for solicited AEs, solicited AEs (recorded by day) need to be converted into the format of unsolicited AEs (recorded by event). All diary data will be considered, as well as any post-dose on-site assessment (scheduled as well as unscheduled) within (including the day of vaccination) 8 days after vaccination. For solicited local AEs for which a diameter is measured, the maximum of diameter derived grade and investigator severity (if available) will be used. The start date of the AE will be considered as the date of first occurrence of the solicited AE (both local and systemic). If on subsequent day(s), the same grade is reported, the last reported date is used as the end date of the AE. A new record is created in case the grade of the event changes. If there is a time gap of at least one day between two (or more) occurrences of the same type of the solicited AE, then the second (and/or next) occurrence will be considered as a new AE. In case no data is reported for a day, this is analyzed as no event reported. If the on-site assessment differs in grade or relatedness (if collected) with the corresponding diary data, only the highest grade and the relatedness that most implicates the vaccine per AE will be kept in the analysis database and used in the tables and listings. The following example shows how the solicited AE should be converted into a format of unsolicited AEs:

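### The SAP drops the protocol's assessed-subjects denominator for solicited adverse events without declaring it and discards ungraded reports, so primary reactogenicity rates can only be lowered or left unchanged

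*SAP*

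**What the plan says.** Solicited events are a primary endpoint. Protocol 9.2.1 lists "Solicited local and systemic adverse events (reactogenicity) until 7 days after each study vaccine administration".

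Protocol 11.4 says who is analysed for them: "those subjects in the Full Analysis set for whom reactogenicity assessments are available in the database". Its next sentence gives unsolicited events the whole Full Analysis set, so the protocol states two different denominators.

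SAP section 7 includes solicited events in its list of safety data and then says: "The safety and tolerability data will be summarized based on the full analysis set". It narrows this only by dose actually received. For a subject not given Dose 2, "that subject will not be included in the analysis of AEs in the Post-dose 2 period". Neither section 7 nor 7.1.3 requires a dosed subject to have any reactogenicity data.

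SAP 7.1.2 opens with "Missing data will not be imputed" and continues: "If the severity is missing for a solicited AE, then it will not be considered as an AE". The same section treats a missing relationship to vaccine differently: the event stays in and its relationship is labelled unknown. For diary gaps, Attachment 2 says: "In case no data is reported for a day, this is analyzed as no event reported".

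SAP section 3, which records changes to the planned analysis, covers only the immunogenicity and per protocol sets.

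**The concern.** A subject who was dosed but returned no reactogenicity data cannot contribute an event. Under the SAP that subject still adds one to the denominator, which is the same as recording no reaction. The protocol leaves such a subject out. The two documents therefore give different percentages for a primary endpoint whenever such subjects exist, and nothing in the SAP tells the reader that the rule has moved.

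The missing-grade rule works on the numerator. A symptom that the subject did report leaves the count if no grade was recorded. This sits awkwardly beside the statement that nothing is imputed, because the effect is to set a missing value to no event.

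No formal testing is planned, so the descriptive percentages are themselves the primary result. Both rules push those percentages in the direction that makes the vaccine look better tolerated.

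**Working it through.** **Stated figures.** Neither document gives a rate of missing diaries or missing grades, so there is no figure to reproduce. The shares below are assumptions.

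**Inputs.**
- Event rates: about three fifths of subjects with a local reaction and two fifths with a general symptom after MVA-BN-Filo (protocol 1.1.2.2), used as 60% and 40%.
- Group size for illustration: 174 active subjects, as planned for Groups 1 and 2 (protocol 11.2). Actual numbers are lower, since recruitment stopped at about 423 in total (SAP 1.4).
- m: share of dosed subjects with no reactogenicity data after that dose (assumed).
- g: share of events with no grade on any record (assumed).

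**Denominator.** Let p1 be the event rate among subjects with data and p0 the rate among those without.
- True rate = (1 − m)p1 + m·p0
- SAP rate = (1 − m)p1, which is too low by m·p0. This is never negative.
- Protocol rate = p1, which is off by m(p1 − p0). This is zero if missingness is unrelated to outcome.

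With p1 = p0 = p, the SAP reports p(1 − m):

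| m (assumed) | true 60% reported as | true 40% reported as |
|---|---|---|
| 0 | 60.0% | 40.0% |
| 1% | 59.4% | 39.6% |
| 5% | 57.0% | 38.0% |
| 10% | 54.0% | 36.0% |

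In whole subjects with n = 174 and m = 5%, 165 have data and 99 of them have an event. The protocol denominator gives 99/165 = 60.0% (exact 95% CI 52.1 to 67.5). The SAP gives 99/174 = 56.9% (49.2 to 64.4).

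**Missing grade.** With both rules the SAP rate is p(1 − m)(1 − g).
- m = 1%, g = 1%: 0.60 × 0.99 × 0.99 = 58.8%. Correcting only the denominator gives 0.60 × 0.99 = 59.4%.
- m = 5%, g = 2%: 0.60 × 0.95 × 0.98 = 55.9%. Correcting only the denominator gives 0.60 × 0.98 = 58.8%.

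Restoring the protocol denominator therefore does not undo the missing-grade rule.

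**Blank diary days.** The incidence table counts subjects with at least one occurrence. A blank day matters only if every day of the event is blank and no site assessment records it. With independent daily non-reporting of 5% (assumed), a one-day event is lost with probability 0.05 and a two-day event with probability 0.05² = 0.0025. Calling the day missing instead of event-free changes neither the numerator nor the denominator of that table.

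**The case against.** The best defence is that SAP section 7 is a general statement. Protocol 11.1 makes the same one for safety data, and 11.4 then refines it, so the SAP may simply have left out the refinement. That is a fair reading of intent. The SAP is nevertheless the document that will be programmed, and as written it has no such condition.

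The defence on size is stronger. After each dose, subjects are observed at about 30 and 60 minutes and solicited events are documented. Site staff review the diary 3 and 7 days later, when the injection site is also examined, and the diary is to be completed on site at the second of these visits (protocol 9.1.4 and 9.2.2). Attachment 2 uses on-site assessments within the 8-day window. Few subjects should have no data at all. This stands. It also shows that if the 60-minute observation alone counted as an assessment, the protocol's denominator would be almost the full analysis set.

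On missing grades, SAP 7.1.1 accepts either a diameter-derived or an investigator grade, so a measured reaction is ungraded only if both are missing. Reactions below mild are not adverse events, and erythema and induration/swelling are graded by diameter only from 2.5 cm. Counting every ungraded skin reaction would let in some that fall below the threshold. This stands for diameter-graded reactions, but not for symptoms such as headache or myalgia.

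The protocol's denominator also carries an assumption: if subjects without data had fewer reactions, it would overstate the rate. This is true, and is a reason to show how many are excluded.

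**Conclusion.** The point holds. The SAP's denominator for a primary endpoint departs from protocol 11.4 without being declared, and the missing-grade rule drops reported symptoms. Both act in one direction only. With complete, graded data the effect is zero. Its real size cannot be worked out from the documents and is probably small. The illustrative losses for a 60% rate, 0.6 points at m = 1% and 3 points at m = 5%, rest on an assumed m and on missingness unrelated to outcome.

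A reader might infer more than this, in three ways that the documents do not support:
- That the primary rates are known to be materially too low. No completeness figure is given, and the site procedures argue against a large m.
- That all the missing-data rules contradict the protocol. Only the denominator does; protocol section 11 is silent on missing grades and blank days.
- That the active versus placebo contrast is distorted. The same rules apply to both arms, so this depends on whether missingness differs between them.

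Severity is minor to moderate.

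**What to change.** 1. In SAP 7 and 7.1.3, use the protocol 11.4 denominator for solicited events, separately for each dose. Define it by reactogenicity data beyond the 60-minute observation: at least one diary day, or a site assessment at the visit 3 or 7 days after that dose. Show the number excluded by schedule and by active or placebo. If the full analysis set is preferred, declare and justify the change in SAP section 3.
2. In SAP 7.1.2, keep a reported solicited symptom with no grade from any source in the any-grade count, labelled grade unknown, as is already done for a missing relationship. Make an exception for erythema and induration/swelling: report ungraded cases as a separate count, because an unmeasured reaction may fall below the grade 1 threshold.

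A table limited to complete diaries is optional. Relabelling blank days is not needed for the incidence table.

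The cost is SAP wording and a few extra counts, with no new data. Reported rates may come out slightly higher.
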